3.2 Exclusion Criteria for focus groups

3.2.1 Adults/Adolescents

- 3.2.1.1 Inability or unwillingness of research participant or legal guardian/representative to give written informed consent.

3.3 Inclusion Criteria for feasibility study

- 3.3.1 Hispanic, non-Hispanic Black, and non-Hispanic White 10–17-year-old survivors of pediatric cancer
- 3.3.2 At least one-year post treatment completion
- 3.3.3. Pain present over the past 3 months and pain at least once per week
- 3.3.4. Pain interfering with at least one area of daily functioning

3.4 Exclusion Criteria for feasibility study

- 3.4.1. Limb amputation
- 3.4.2. History of seizure disorder or other neurological disorders
- 3.4.3. Presence of metallic intracranial implants (neurostimulator, Ommaya reservoir, CSF shunt, or aneurysm clip), and metallic and non-metallic cranial, excluding the bones of the face and jaw, prosthesis (implants/plates).
- 3.4.4. Serious comorbid psychiatric condition
- 3.4.5. Current substance abuse
- 3.4.6. History of development delay or significant cognitive impairment
- 3.4.7. History of brain tumor diagnosis

3.5 Research Participant Recruitment and Screening

Four institutions will collaborate in the proposed protocol: St. Jude Children's Research Hospital (SJCRH); Children's Healthcare of Atlanta (CHOA), Texas Children's Hospital (TCH); and Seattle Children's Hospital (SCH). The three sites will provide contact information only for potential participants. SJCRH will screen, recruit, and consent all eligible participants for the study.

3.6 Enrollment on Study at St. Jude

A member of the study team will confirm potential participant eligibility as defined in Sections 3.1-3.2 and complete the 'Participant Eligibility Checklist' in OnCore if required by the study team. Eligibility will be reviewed, and a research participant-specific consent form and assent document (where applicable) will be generated. The entire signed consent/assent form(s) must be scanned into the Electronic Health Record (EHR) by the study team designee.

3.7 Procedures for Identifying and Screening Participants

Prior to initiating the study, a workshop will be held by SJCRH with team members from all sites participating. The background to the study, study procedures, consent processes, data transfer, and plans to monitor intervention integrity and data quality will be the content for that workshop.

Following the workshop and preparation of sites for identifying potentially eligible research participants will begin. Eligibility of newly admitted research participants will be confirmed during daily discussions between the study investigators, research assistants, and attending physician for both the Solid Tumor and Leukemia teams.

4.0 DESIGN AND METHODS

4.1 Design and Study Overview

This study will include the (1) cultural adaptation of an evidence-based mobile CBT program for chronic pain and procedures for tDCS and (2) a feasibility study of adapted mobile CBT paired with tDCS. Participants will be recruited from four large pediatric cancer centers: St. Jude Children's Research Hospital (SJCRH), Children's Healthcare of Atlanta (CHOA), Texas Children's Hospital (TCH), and Seattle Children's Hospital (SCH). Collaborating sites will provide SJCRH with potential participant contact information and SJCRH will consent and enroll participants on the study at SJCRH.

Mobile cognitive behavioral therapy for chronic pain: The mobile CBT program we propose to utilize, WebMAP mobile,⁷⁹ was created by [name] (Co-I). The program is available on

[figure not shown]

Figure 2. Screen shots from WebMAP mobile
IRB NUMBER: 22-1185
IRB APPROVAL DATE: 04/02/2024

Android and iOS operating systems and is an interactive, self-guided intervention with six core treatment modules. These modules focus on 1) pain education, 2) stress, emotions, and thoughts (e.g., pleasant activity scheduling, thought stopping), 3) relaxation and imagery, 4) lifestyle and school interventions, 5) staying active, and 6) maintenance and relapse prevention. Within the app, participants complete screening questions to set up a profile and evaluate the need for two supplementary treatment modules focused on comorbidities of negative mood and sleep. There are several functional components to the app, including *places and lessons* (each place has 3-5 lessons that provide education and teach pain management skills), *library* (information on skills presented through audio clips, videos), *check-in* (allowing participants to track their pain, activity, mood, and sleep), and *skills tracker* (participants record practicing specific skills such as sleep relaxation). Screen shots from the app are shown in Figure 2. Content is metered according to a time schedule, requiring youth to spend 5 days on skills practice before an assignment can be completed. Components of the program can be used daily (e.g., check in, skills practice). Total treatment duration is approximately 20 min per week over 6 to 8 weeks depending on the number of supplementary modules assigned. The app uses daily reminder notifications to encourage users to log in and complete assigned tasks. If needed, participants will be provided with a mobile device to access the intervention.

Cultural adaption of mobile CBT: A recent systematic review of cultural adaption of internet- and mobile-based interventions for mental disorders identified specific components necessary for cultural adaptation that fall under 3 key domains: content, methodological, and procedural (see Table 1).⁸⁰ For the current proposal we will culturally adapt mobile CBT, separately for Black and Hispanic survivors of childhood cancer, guided by key domains in Table 1 and identify tailoring variables that will be used to assign adapted intervention content. This will avoid the assumption of complete homogeneity within any one culture. The objective of cultural adaptation is to improve the ecological and external validity of an intervention for a culture group different than the group it was originally intended for. Nonetheless, it is important to retain core components of the program to maintain effectiveness in the target population.⁸¹

Table 1. Key domains and components of cultural adaption of mobile-based interventions for mental disorder⁸⁰

Content
• Illustrations
• Language
• Mental health concepts
Methodological
• Structure of the intervention
• Functionality
• Design and Aesthetics
Procedural
• Methods used to obtain information
• Persons involved

Our cultural adaptation will include five phases: (1) expert consultation, (2) stakeholder feedback, (3) preliminary content adaptation, (4) iterative content adaptation with stakeholder feedback, and (5) finalized adaptation.

All cultural adaptation processes will occur separately, but in parallel, for non-Hispanic Black and Hispanic participants. We will use self-identification/report to determine race/ethnicity. For Phase 1 (expert consultation), experts will include [name] (CBT, chronic pain, WebMAP creator), [name] (tDCS, cancer survivorship), [name] (culture and communication, SDOH), and at least one non-Hispanic Black and one Hispanic parent of an adolescent childhood cancer survivor from the Children's Oncology Group Patient Advocate Committee and St. Jude Children's Research

Cultural Adaptation Phases	
Phase 1 (Expert Panel) consultation to identify potential adaptations to mobile CBT program and preliminary identification of tailoring variables.	Virtual meetings with non-Hispanic Black & Hispanic parents & young adult childhood cancer survivors. (2-3) 1-hour meetings
Phase 2 (Stakeholder Consultation) identify adaptations of intervention content and review preliminary tailoring variables.	Virtual focus groups with non-Hispanic Black & Hispanic adolescent childhood cancer survivors. (2-4) 45-minute sessions
Phase 3 (Preliminary Content Adaptations) based on qualitative analysis based of stakeholder feedback.	Co-investigators make preliminary intervention content adaptations.
Phase 4 (Iterative Content Adaptation) with ongoing stakeholder feedback. Adaptations shared with survivors and additional feedback solicited.	Virtual focus groups with non-Hispanic Black & Hispanic adolescent childhood cancer survivors with chronic pain. Ongoing program content adaptation based on qualitative analysis. (2-4) 45-minute sessions
Phase 5 (Finalized Adaptation) with ongoing stakeholder feedback. Finalized adaptions and tailoring variables shared with survivors.	Virtual focus groups with non-Hispanic Black & Hispanic adolescent childhood cancer survivors who participated in previous sessions. Final program content adaptation based on qualitative analysis. (2-3) 45-minute sessions

Hospital Patient and Family Advisory Council, and at least one Black and one Hispanic young adult childhood cancer survivor (lived experience participants). We will solicit feedback from stakeholders and lived experience participants related to the study design and conduct.

Phase 1 will involve a minimum of two 1-hour meetings to identify possible adaptations including surface (e.g., characters, activities, language), conceptual (e.g., treatment goals, values, mental health concepts) and mobile specific considerations (e.g., amount of human guidance). Preliminary identification of tailoring variables will also be discussed. Non-Hispanic Black and Hispanic participants will meet separately.

Phase 2 (stakeholder consultation), we will recruit 8 to 12 Black and 8 to 12 Hispanic adolescent (10-17 years of age) survivors of childhood cancer who are at least one-year post-treatment completion to serve as initial stakeholders and participate in virtual focus groups. All focus groups will be conducted via an online HIPAA compliant platform, audio-recorded, and transcribed verbatim. Our team has experience conducting focus groups virtually in multiple cultures and languages.^{82, 83} We will engage in purposive sampling to include representation by sex and neighborhood disadvantage as this is an important SDOH related to treatment uptake and engagement. To avoid potential saturation of our sample for the intervention phase, we will not restrict participation in the adaptation phase to bone sarcoma survivors. Focus groups will be conducted by two facilitators who will use a guide/probe structured around the 3 key domains of cultural adaptation, to solicit specific feedback about potential adaptation of the images, concepts, personal stories, daily life examples and preliminary tailoring variables identified during the expert consultation phase. If Hispanic participants indicate that they would prefer a Spanish translation of the entire program or specific components (e.g., videos) this be incorporated into the adaption process. [name] is fluent in Spanish and has research assistants who are native Spanish speakers trained to conduct focus groups; therefore, we will be able to provide focus groups in Spanish or with staff who are bilingual, if preferred by stakeholders. We plan to hold approximately three 45-minute sessions over a at least a 3-week period to allow for sufficient time to review all program material. We will hold separate focus groups for non-Hispanic Black youth and for Hispanic youth.

Phase 3 We will make preliminary content adaptations based on results of our qualitative analysis of stakeholder feedback (see analytic description below) and create mock- ups to demonstrate these adaptations. We will show how identified culturally relevant tailoring variables (e.g., family involvement, spirituality, values, amount of guidance) can assign adapted intervention content (e.g., tailored vignettes) or functionality. For example, if religiosity is deemed an important tailoring variable, character stories will be tailored to incorporate prayer and religious social support. Any proposed changes to app functionality (e.g., amount of human guidance) will be considered at this phase.

Phase 4 This will be an iterative adaptation process where we demonstrate our proposed adaptations to stakeholders. We will refine the adaptations by eliciting rapid iterative feedback from youth in three cycles, with 5-7 Black and 5-7 Hispanic adolescent survivors of childhood cancer who have a history of chronic pain participating per cycle (n=15-21 total). This will allow us to be

informed by survivors with lived experience of chronic pain. We will again engage in purposive sampling to include representation by sex and neighborhood disadvantage. We plan to hold approximately three sessions (about 45-minutes each) with adequate time in between to work with our programming team to make modifications to app mock-ups. Importantly, because this group of stakeholders will have chronic pain, these focus groups will specifically emphasize the acceptability of adapted vignettes and pain management practice skills. This phase also will allow for refinement of tailoring variables.

Phase 5 will involve approximately two meetings with 5-7 non-Hispanic Black and 5-7 Hispanic adolescent survivors of childhood cancer who participated in earlier phases to present the adapted interventions from the results of focus groups and rapid feedback cycles. Feedback will be collected and analyzed to inform any further changes.

Transcranial direct current stimulation

(tDCS) – Mobile System: For remotely supervised tDCS stimulation, we will employ a procedure consistent with recently published professional guidelines⁸⁴ and with those utilized in our ongoing NEUROSTIM and

ALLSUP studies. The mobile tDCS system is manufactured by Soterix Medical and consists of a rechargeable lithium battery pack, handheld control unit and a self-positioning headband with electrodes (Figure 3). This device is specifically designed for remote studies. It has an easy set-up and allows for precise reproduction of electrode positioning. This system allows for double-blind application of the intervention or sham treatments through the use of single-use passcodes. An anodal electrode will be placed over the dorsolateral prefrontal cortex (equivalent to F3 and F4 electrode sites) on the side of the body reported to experience the most pain, with a cathode reference electrode placed at the supraorbital region ipsilateral to the side of the body reported to experience the most pain. The electrodes are single-use and snap into pre-configured fixed locations of a flexible headband that is individualized for each participant. Participants will complete training via a telehealth platform that includes instruction on how to connect the electrodes, place the headband, and operate the device. As part of this training, participants will complete a single session of tDCS treatment.

Figure 3. tDCS handheld control unit and preconfigured headband

During active sessions participants will receive 1mA direct current flow for 20 minutes. Sham sessions provide a ramp up to 1mA direct flow over a 5 second interval and return to no current flow for the remainder of the session. The tDCS unit requires a unique code for each stimulation session. Each remote session will be monitored for adherence and tDCS device connection quality. If needed, participants will be supplied with a device (iPad, laptop) to allow for video monitoring of the sessions. This methodology is consistent with the approach successfully utilized in our pilot study and ongoing studies. Cultural considerations: While the extent of cultural adaptation that can be applied to tDCS is, unfortunately, limited, we will utilize the above-described focus groups to discuss tDCS. We will conduct a 4th focus group during each phase dedicated exclusively to tDCS procedures. We will solicit feedback from stakeholders on acceptable language to describe tDCS and obtain feedback on study materials (e.g., handouts, images, instructions) and procedures (e.g., family involvement). In our ongoing study, NEUROSTIM, we have made adaptations to tDCS head straps to accommodate different hairstyles and will solicit feedback on the appropriateness of this and other adaptations across cultures.

Feasibility Study: Eligible participants will be assigned to either culturally adapted mobile CBT + active tDCS to the DLPFC or culturally adapted mobile CBT + sham. For the pilot phase, 10 participants will be enrolled from each racial and ethnic group (non-Hispanic Black, Hispanic, non-Hispanic White), and 5 participants in each group will be allocated to receive active tDCS and 5 to sham tDCS. We will alternate assignment of tDCS location within each group as participants are enrolled using an ABAB design for treatment allocation, separately for each racial and ethnic group. Because this is a feasibility study, blocked randomization and blinding is not necessary, but will be employed in a later study. Participants will complete two 20-minute stimulation sessions per week for 6 weeks. Each week, tDCS sessions will be paired with the mobile CBT program (e.g., core content, practice skills) at a time that is convenient to the participant. Two sessions will not occur within the same 24-hour period. As described above, participants will receive a unique activation code prior to each stimulation session. Each active session will be pre-programmed to deliver 1mA of direct current for 20-minutes; each sham session will be programmed to provide a ramp up to 1mA over a 5 second interval and no current flow for the remainder of the session. tDCS parameters cannot be changed by participants. Adolescents will complete the outcomes measures listed below (e.g., pain intensity, functional disability) and parents will complete measures of SES, anxiety, depression, and their child's medication use at baseline and post-intervention.

Adverse event monitoring: Patient reports of AEs will be surveyed weekly, with symptoms reported for the prior tDCS sessions. Information will be collected by incident participant reporting and direct questioning using the patient report of incidence of side effects (PRISE).⁸⁵ Side effects will be assessed during weekly sessions. The PRISE assesses the presence of side effects for several biological systems. For each system (skin, nervous, eyes/ears, sleep, other), participants indicate the presence of a side effect, and if present, the tolerability of the side effect (tolerable or distressing). The PRISE includes commonly reported side effects of tDCS: tingling, itching sensation, burning sensation, pain, headache, fatigue, difficulty concentrating, and nervousness.⁸⁶ Participants will also be asked to report any other symptoms experienced during the tDCS session.

Figure 4a. Study Schema – Virtual Focus Groups

[figure not shown]
[figure not shown]

Figure 4b. Study Schema – Feasibility Pilot Study

4.2 Study Procedures:

All cultural adaptation processes will occur separately, but in parallel, for non-Hispanic Black and Hispanic participants. See detailed descriptions of procedures in 4.1 Design and Study Overview above.

Expert Panel via virtual meetings - 2 to 4 (1) hour virtual meetings with non-Hispanic Black and Hispanic parents and young adult survivors of childhood cancer and key study investigators. Sessions will be audio-recorded and transcribed verbatim.

Stakeholder Focus Group via virtual focus groups - (2-4) 45-minute sessions with non-Hispanic Black and Hispanic adolescent survivors of childhood cancer. Sessions will be audio-recorded and transcribed verbatim.

Preliminary Content Adaptations – based on results of qualitative analysis of stakeholder feedback.

Iterative Adaptation Process via virtual focus groups - (2-4) 45-minute sessions where adaptations will be presented to lived experience stakeholders (non-Hispanic Black and Hispanic survivors of childhood cancer with chronic pain). Sessions will be audio-recorded and transcribed verbatim.

Feedback meetings via virtual focus groups – (2-3) with 5-7 non-Hispanic Black and 5-7 Hispanic adolescent survivors who participated in previous sessions to review final program adaptations. Sessions will be audio-recorded and transcribed verbatim.

Mobile Cognitive Behavioral Therapy (CBT) - for chronic pain: Participants in the stakeholder focus group and the feasibility study will use mobile CBT program, WebMAP. Available on Android and iOS operating systems, this

program is interactive, self-guided intervention with six core treatment modules. These modules focus on 1) pain education, 2) stress, emotions, and thoughts (e.g., pleasant activity scheduling, thought stopping), 3) relaxation and imagery, 4) lifestyle and school interventions, 5) staying active, and 6) maintenance and relapse prevention. Within the app, participants complete screening questions to set up a profile and evaluate the need for two supplementary treatment modules focused on comorbidities of negative mood and sleep. There are several functional components to the app, including *places and lessons* (each place has 3-5 lessons that provide education and teach pain management skills), *library* (information on skills presented through audio clips, videos), *check-in* (allowing participants to track their pain, activity, mood, and sleep), and *skills tracker* (participants record practicing specific skills such as sleep relaxation).

Stakeholders in the focus groups will offer specific feedback about potential cultural adaptation of the images, concepts, personal stories, daily life examples and preliminary tailoring variables following proposed changes from the expert panel.

During the feasibility study phase eligible adolescent participants with chronic pain will be asked to use the CBT program with tDCS 20 minutes a day, twice a week for 6 weeks.

Transcranial Direct Current Stimulation (tDCS) Eligible participants will be assigned to either culturally adapted mobile CBT + active tDCS to the DLPFC OR culturally adapted mobile CBT + sham. For the feasibility phase, 10 participants will be enrolled from each racial and ethnic group (non-Hispanic Black, Hispanic, non-Hispanic White), and 5 participants in each group will be allocated to receive active tDCS and 5 to sham tDCS. We will alternate assignment of tDCS location within each group as participants are enrolled using an ABAB design for treatment allocation, separately for each racial and ethnic group. Because this is a feasibility study, blocked randomization and blinding is not necessary, but will be employed in the R33 phase. Participants will complete two 20-minute stimulation sessions per week for 6 weeks. Each week, tDCS sessions will be paired with the mobile CBT program (e.g., core content, practice skills) at a time that is convenient to the participant. Two sessions will not occur within the same 24-hour period. As described above, participants will receive a unique activation code prior to each stimulation session. Each active session will be pre-programmed to deliver 1mA of direct current for 20-minutes; each sham session will be programmed to provide a ramp up to 1mA over a 5 second interval and no current flow for the remainder of the session. tDCS parameters cannot be changed by participants. Adolescents will complete the outcomes measures listed

below (e.g. pain intensity, functional disability) and parents will complete measures of SES, anxiety, depression, and their child's medication use at baseline and post-intervention.

During the stakeholders focus groups, participants will be asked to give feedback to the extent cultural adaptation can be applied to tDCS. **During the feasibility study phase** eligible adolescent participants with chronic pain will be asked to use the CBT program with tDCS 20 minutes a day, twice a week for 6 weeks.

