
Brief Overview: This study will include (1) cultural adaptation of an evidence-based mobile cognitive behavioral therapy (CBT) program for chronic pain and procedures for transcranial direct current stimulation (tDCS) and (2) a feasibility study of adapted mobile CBT paired with tDCS. Participants will be recruited from four large pediatric cancer centers: St. Jude Children's Research Hospital (SJCRH), Children's Healthcare of Atlanta (CHOA), Texas Children's Hospital (TCH), and Seattle Children's Hospital (SCH). CHOAs, TCH, and SCH will provide the study brochure, and if willing, participants will complete a Consent to Contact form. SJCRH will screen, consent, and conduct all study procedures for all eligible participants for the study.

Intervention: We will conduct a series of focus groups with non-Hispanic Black and Hispanic childhood cancer survivors to obtain their input on culturally adapting a mobile CBT program for chronic pain and tDCS procedures. Once this adaptation process is completed, we will conduct a feasibility trial with non-Hispanic Black, Hispanic and non-Hispanic White childhood cancer survivors with chronic pain.

Study Design: Prospective study employing focus groups to culturally adapt CBT and tDCS procedures which will then be used for the second phase, a feasibility study. The feasibility study will assign eligible participants to either culturally adapted mobile CBT + active tDCS to the dorsolateral prefrontal cortex or culturally adapted mobile CBT + sham tDCS.

Sample Size: We anticipate approximately 60 participants for the focus groups and approximately 30 participants for the feasibility study for a total of about 90 participants.

Data Management: The Study Team at SJCRH will design forms for data collection within the electronic database. Statistical analysis will be provided locally by the Biostatistics Department at St. Jude Children's Research Hospital.

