4.3 Study Measures/Observations

Participants in both the focus group and feasibility study will be asked to fill out screening questions as described in the paragraph below.

Demographics: Participants will complete a consent to contact form and, if willing, will complete demographics questions during the screening process to obtain ethnicity, race, and other information needed to target recruitment to meet enrollment goals. If we are unable to confirm diagnosis or other screening information needed to confirm eligibility, study staff will ask the parent/guardian to sign a medical release form to obtain pertinent medical records.

Participants in the feasibility study will complete the outcomes measures listed below (e.g. pain intensity, functional disability) and parents will complete measures of SES, anxiety, depression, and their child's perception of pain and medication use at baseline and post-intervention (Table 2)

Pain intensity and pain interference: The *Brief Pain Inventory-Short Form* (BPI) includes a 4-item pain severity scale.⁸⁷ Participants rate their worst and least pain in the last week, average pain, and current pain.⁸⁸ The BPI pain intensity has good internal consistency in survivors of childhood cancer ($\alpha=0.87$).⁸⁹ This measure includes a body diagram to allow participants to indicate where they experience the most pain. This will be used to inform placement of the anodal tDCS electrode (i.e., right vs. left DLPFC).^{90, 91}

Pain catastrophizing: The *Pain Catastrophizing Scale, Child version* (PCS-C)⁹² is a 13-item self-report measure of overly negative attitudes of pain and it consists of three scales of rumination, magnification, and helplessness. Higher scores indicate more pain catastrophizing.⁹³ This measure has good reliability (Cronbach's $\alpha=0.90$) in a clinical sample of children and adolescents with chronic or recurrent pain.⁹² The *Pain Catastrophizing Scale, Parent version* (PCS-P) is a

modified version of the PCS-C based on parent report of their own catastrophizing related to their child's pain. It assesses the same three factors of rumination, magnification, and helplessness.^{94, 95}

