Finally, we will estimate preliminary effectiveness of the intervention to inform potential changes to the proposed sample size needed for the larger R33 clinical trial. We will compare mean change scores for pain intensity and functional disability in survivors who received active tDCS vs. sham using a two-sample t-test. Although we will not be powered to detect a statistically significant difference between the groups, we will use the effect estimate to inform power calculations for the R33 clinical trial. If any of the feasibility parameters including 1) participation rate, 2) adherence, or 3) acceptability do not meet our a priori defined feasibility definitions, we will re-engage stakeholders and individuals with lived experiences for input and make adaptions to the interventions based their feedback as well as data we collect from participants related to reasons drop out and unfavorable acceptability. Transition to the R33 phase will be contingent on meeting milestones defined in the Study Timeline. These include: 1) adaptation and tailoring of intervention content, 2) completion of mobile CBT program modifications, and 3) completion of the 6-week feasibility trial of culturally adapted CBT + tDCS.

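### Active or sham tDCS is assigned by foreseeable ABAB alternation with blinding declared unnecessary, yet the active-versus-sham estimate is to inform power for the R33 trial

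*Combined protocol and SAP*

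**What the plan says.** The Feasibility Study part of Section 4.1 plans 10 participants in each of three racial/ethnic groups, 5 to active and 5 to sham. The method is: "We will alternate assignment of tDCS location within each group as participants are enrolled using an ABAB design for treatment allocation", done separately by group. On randomization and blinding it says: "Because this is a feasibility study, blocked randomization and blinding is not necessary, but will be employed in a later study". Section 4.2 repeats this and names the later study: "Because this is a feasibility study, blocked randomization and blinding is not necessary, but will be employed in the R33 phase".

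The synopsis puts all contact with participants at one centre: "SJCRH will screen, consent, and conduct all study procedures for all eligible participants for the study". Section 4.1, on the mobile tDCS system, says of the device: "This system allows for double-blind application of the intervention or sham treatments through the use of single-use passcodes".

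Section 9.0 pools all 30 participants for the completion rule. It then plans a two-sample t-test of mean change in pain intensity and functional disability, active against sham. It accepts that this is not powered. The stated purpose is "to inform potential changes to the proposed sample size needed for the larger R33 clinical trial", and it adds that "we will use the effect estimate to inform power calculations for the R33 clinical trial".

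**The concern.** Alternation by enrolment order lets anyone who knows the rule and one past assignment in a group foresee every later one. Race and ethnicity are collected at screening (Section 4.3), so the group is known before enrolment. Whether and when to approach or enrol a given survivor can then depend, even unintentionally, on the arm that comes next.

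Pain is self-rated, so knowing the arm can move the outcome through expectation. A sham arm exists largely to control for that, and without blinding it loses much of this function.

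The reason given is that this is a feasibility study. That covers the completion rule but not the between-arm estimate. At stake is whether that estimate measures what a randomized, blinded R33 trial would measure, or mixes any tDCS effect with biases that R33 would largely exclude.

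There is also a wording conflict. The allocation sentence says that tDCS location is alternated, whereas the arms differ by active or sham stimulation. Section 4.1 (mobile system) ties electrode placement to the more painful side, and Section 4.3 says of the body diagram: "This will be used to inform placement of the anodal tDCS electrode (i.e., right vs. left DLPFC". These passages must be reconciled.

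**Working it through.** **The plan's own figure.** Section 9.0 gives a lower bound of 0.61 for 23 completers of 30. The exact one-sided 95% Clopper-Pearson bound is the 5th percentile of Beta(23, 8) = 0.606, which rounds to 0.61. It uses both arms pooled, so it does not depend on how arms are assigned. The plan states no power or precision for the active-sham comparison.

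**Predictability of assignment** (3 groups of 10, 5:5 in each; Section 4.1)

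- ABAB: once the first assignment is seen, 9 of 10 are fixed, and 3 × 9 = 27 of 30. If the starting arm is also known, 30 of 30.
- Random list with past assignments hidden: 50%, or 15 of 30.
- Random list with all past assignments visible, guessing the under-represented arm:
  - blocks of 2: (0.5 + 1)/2 = 75%
  - blocks of 4: (0.5 + 0.667 + 0.667 + 1)/4 = 71%
  - one 5:5 ordering of 10: 6.53/10 = 65%

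Randomizing without masking therefore helps only in part. Most of the gain comes from concealment and blinding.

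**Precision at 15 versus 15.** SE of a standardized difference d = √(1/15 + 1/15 + d²/60).

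- At d = 0: 0.365.
- At d = 0.54: √(0.1333 + 0.0049) = 0.372.
- 95% CI for an observed 0.54: 0.54 ± 1.96 × 0.372 = −0.19 to 1.27.

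The 0.54 is the size of the meta-analytic effect for DLPFC stimulation quoted in Section 2.1, read here as a standardized difference. It is used only for illustration.

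**What a bias could do.** The documents give no bias figure, so upward biases b of 0.1, 0.2 and 0.3 SD are assumed. Share of mean squared error = b²/(b² + 0.372²). R33 is assumed to use a two-sample t-test, two-sided 0.05, 80% power, and to be sized on the biased estimate alone, with a true effect of 0.54.

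| Assumed bias (SD) | Share of MSE | Estimate used | R33 n per arm | True power |
|---|---|---|---|---|
| 0 | 0% | 0.54 | 55 | 80% |
| 0.1 | 7% | 0.64 | 40 | 66% |
| 0.2 | 22% | 0.74 | 30 | 54% |
| 0.3 | 39% | 0.84 | 24 | 45% |

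**Sampling error for comparison.** An unbiased estimate one SE too high is 0.54 + 0.37 = 0.91. Sizing on it gives 20 per arm and 38% true power.

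**The case against.** The choice is deliberate and disclosed, and the plan defers randomization and blinding to the later trial. The quantitative objective is feasibility, the completion rule pools the arms, and the milestones for moving to R33 do not include the active-sham contrast. All of that stands, and it limits the point to one unpowered analysis. It does not answer the point, because the plan still gives that estimate a job.

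Sampling error dominates. Biases of 0.1, 0.2 and 0.3 SD raise the root-mean-square error by only about 4%, 14% and 28% (√(1 + b²/0.372²)). With a true effect of 0.54, an unbiased 15-versus-15 comparison would show 0.74 or more about 30% of the time. This also stands, and it is a reason not to size R33 on the estimate alone even after the fix. But a confidence interval displays imprecision and does not display bias.

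The plan refers to changing an already proposed R33 sample size, so the estimate is one input among others. The power figures above are therefore conditional, not a forecast. Bias could also run downward.

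The documents are silent on concealment and on whether participants are told their arm. A ramp-up sham and a code for each session are compatible with participants not knowing. Expectation bias is therefore a risk, not a certainty. Naming one centre does not show that the staff who obtain consent see the running sequence. Even so, strict alternation within known groups is foreseeable, and nothing in the plan prevents staff from using it.

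**Conclusion.** The concern holds. The allocation is foreseeable for at least 27 of 30 participants, blinding is set aside although the device supports it, and the resulting between-arm estimate is meant to inform power for a trial that will be randomized and blinded. The estimate is open to avoidable selection bias, and to expectation bias if arms become known. How large either would be cannot be derived from the documents. The fall in R33 power to 66%, 54% or 45% rests on the assumed bias sizes, an upward direction, a true effect of 0.54 SD and sizing on this estimate alone.

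The consequence is confined to one secondary analysis. The 23-of-30 rule and the R33 transition milestones are not affected. This should be changed, but it does not undermine the feasibility aim.

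**What to change.** Preferred change:

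- Replace ABAB with a concealed random list prepared by the Biostatistics Department, stratified by racial/ethnic group with 5:5 in each 10 (for example, permuted blocks in random order).
- Have the single-use active and sham passcodes issued by staff outside recruitment and outcome collection, so that participants, parents and session and assessment staff are blinded. Add an unblinding procedure for safety events.
- Reword the allocation sentence in Sections 4.1 and 4.2, for example: *Within each racial and ethnic group, participants will be assigned to active or sham tDCS from a concealed random list.* Reconcile it with the passages that set electrode side by the painful side.
- In Section 9.0, report the active-sham difference with its 95% CI and state that it will not size R33 on its own.

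If alternation without blinding is kept, state in Section 9.0 that the difference is descriptive only and will not be used for R33 power.

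Cost: protocol wording, a short list and a rule on who holds the passcode key. The sample size, 5:5 split and device stay the same. The documents do not show whether staff separate from recruitment and assessment are available, so the sponsor must confirm this. The preferred change removes avoidable bias but not the sampling error of 15 versus 15. The fallback costs one sentence.
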